10.2.5.3 Clinical Laboratory Evaluations

Clinical laboratory evaluations include the continuous variables for hematology, serum chemistry, and urinalysis. Laboratory values will be presented in International System of Units. The baseline laboratory value will be defined as the last value before or on the day of the first dose of either study drug. The on-treatment period will be defined as the day after the first dose of either study drug to 28 days after the last dose of rociletinib or MPDL3280A. Laboratory values collected during the on-treatment period will be included in the summary tables. The laboratory values collected after the on-treatment period will only be presented in the data listings.

The summary of laboratory data will include descriptive statistics (N, mean, standard deviation, minimum, median, and maximum) of the maximum, minimum, and last value during the treatment period by dose group and study phase. Summaries using descriptive statistics of the change from baseline to the maximum, minimum, and last value during the on-treatment period will also be given by dose group and study phase. Separate listings will be produced for clinically significant laboratory abnormalities (ie, those that meet Grade 3 or 4 criteria according to CTCAE) by dose group.

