HIV/HBV/HCV serology ^R	Х							
ECHO/MUGA ^s	Х							
12-lead ECG ^T	\mathbf{X}^{F}	Х	X	X	X	X	X	
Pulmonary function test ^U	X							

			Treatment Period					
	Screening Period	Rociletinib 7-day Run- In- Period (Phase 1 only)	Cycle 1 combination therapy (21-day cycle) Cycle 2+ combination therapy (21-day cycle)			Cycle 2+ combination therapy (21-day cycle)	End of Treatment ^C	Follow Up
Procedure ^A	Day -28 to Day 0	Day 1 ^B	Day 1 ^B	Day 4	Days 8 and 15 ±2 days	Day 1 ±3 days		
Tumor biopsy ^V	Х						X ^{C,V}	
Tumor assessments ^W	Х					Х	$\mathbf{X}^{\mathrm{C},\mathrm{W}}$	
Pharmacogenomic blood sample (predose)		Х	X (Phase 2 only)					
Rociletinib PK sampling ^X		Х	Х		Days 8-9	X (see Table 2)	X ^{C,X}	
MPDL3280A PK sampling ^x			X			X (see Table 2)	X ^{C,X}	Х
ATA testing ^X			Х			X (see Table 2)	X ^{C,X}	Х
TBNK blood sample ^X	X ^F		Х		X		X ^{C,X}	
Pharmacodynamic blood sample ^X	Х		X		Day 8	X (see Table 2)	X ^{C,X}	
Dispense rociletinib/ drug accountability/diary ^Y		Х	X			Х		
Rociletinib in-clinic administration ^Y		Х	X		Day 8	Х		
MPDL3280A administration ^Z			X			Х		
Adverse events ^{AA}	Х	Х	Х	Х	X	Х	Х	
Concomitant medications ^{BB}	X	Х	X	X	X	Х	X	
Survival assessment/ subsequent therapies ^{CC}							Х	X

ATA, anti-therapeutic antibody; ECG, electrocardiogram; ECOG, Eastern Cooperative Oncology Group; EGFR, epidermal growth factor receptor; HBV, hepatitis B virus; HCV, hepatitis C virus; HIV, human immunodeficiency virus; MUGA, multigated acquisition (scan); PK, pharmacokinetic; TBNK, T, B, and natural killer; TSH, thyroid-stimulating hormone.

А	Unless otherwise specified: Clinic visits for the specified assessments in Cycle $2+$ should be completed ± 3 days of the scheduled time point relative to C1D1.
	Assessments are to be performed prior to administration of study treatment, when applicable. All results must be reviewed by the Investigator prior to administration
	of study treatment. Perform assessments as scheduled on C1D4 (ie, no window) and assessments for C1D8 and C1D15 within ± 2 days of the scheduled time points.
В	Procedures required on Day 1 of Run-in-Period (Phase 1) or CIDI (Phase 2) may be omitted if completed < 3 days earlier during the Screening Period.
С	Patients will be asked to return to the clinic 28 days (+7 days) after the last dose of study treatment, or before the patient initiates another anticancer agent, if sooner,

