8.2.2 End-of-Treatment Visit

Patients will be asked to return to the clinic for the EOT Visit 28 days (+7 days) after the last dose of study treatment, or before the patient initiates another anticancer agent (if sooner), to assess safety of the patients. Safety evaluation assessments for the EOT Visit are outlined in Table 1. All AEs (including SAEs and protocol-defined events of special interest), regardless of attribution, will be recorded until 28 days after the last dose of study treatment or until initiation of another anticancer therapy, whichever occurs first. Ongoing AEs considered related to study treatment and all SAEs, regardless of causality, will be followed until the event has resolved to baseline grade, the event is assessed by the Investigator as stable, new anticancer treatment is initiated, the patient is lost to follow up, the patient withdraws consent, or it is determined that the study treatment or participation is not the cause of the AE.

Tumor assessment scans do not need to be repeated if radiographic disease progression has been documented previously or the last scans were performed < 2 weeks before the last dose of study treatment or the patient had disease progression at the last scan. For patients who provide additional consent, an optional fresh tumor biopsy will be collected at the time of permanent treatment discontinuation due to disease progression (at the time the Investigator believes the patient is no longer deriving clinical benefit from study treatment, if treatment beyond radiographic disease progression is approved). This optional biopsy and associated blood samples scheduled for the EOT Visist (see Table 2) should occur as close as possible to the date of the decision to permanently discontinue study.

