10.2.5.4 Vital Sign Measurements

The baseline vital sign measurement will be defined as the last value before or on the day of the first dose of either study drug. The on-treatment period will be defined as the day after the first dose of either study drug to 28 days after the last dose of rociletinib or MPDL3280A Vital sign measurements collected during the on-treatment period will be included in the summary tables.

The vital sign measurements collected after the on-treatment period will only be presented in the data listings.

The summary of vital sign data will include descriptive statistics (N, mean, standard deviation, minimum, median, and maximum) of the maximum, minimum, and last value during the on-treatment period by dose group and study phase. Summaries using descriptive statistics of the change from baseline to the maximum, minimum, and last value during the on-treatment period will also be given by dose group.

10.2.5.5 12-Lead Electrocardiograms

Electrocardiogram (ECG) intervals will be stratified into categories indicative of potential clinical significance. Each patient's maximum QT and QT_C intervals from the pretreatment visit and treatment period visits will be classified as $\leq 450 \text{ ms}$, $> 450 \text{ to} \leq 480 \text{ ms}$, $> 480 \text{ to} \leq 500 \text{ ms}$, and > 500 ms. For each patient's maximum change from the pretreatment ECG visit for QT and QT_C, intervals will be classified into < 30 ms, $\geq 30 \text{ to} < 60 \text{ ms}$, and $\geq 60 \text{ ms}$. The number and percentage of patients in each classified category will be presented. Additional endpoints will include abnormal T waves and U waves and other ECG intervals and diagnostic parameters.

Descriptive statistics will be used to summarize other ECG parameters of PR, QRS, QT, and RR interval, and the corresponding changes from pretreatment ECG visit at each time point. Plots of the mean QT/QT_C over time will be provided.

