11 PATIENT DISPOSITION

11.1 Permanent Discontinuation of Study Treatment

A patient must be discontinued from all study treatment if any of the following applies:

- Consent withdrawal at the patient's own request or at the request of their legally authorized representative;
- Clinical disease progression where the Investigator believes that the patient will not continue to benefit from study treatment (*Note:* patients will be permitted to continue study treatment after a radiographic progression [Appendix A: and Appendix B] if the benefit-risk ratio is judged to be favorable and continued treatment is approved by the Medical Monitor);
- Any event, adverse or otherwise, that, in the opinion of the Investigator, would pose an unacceptable safety risk to the patient;
- Any requirement for dose holds of rociletinib for more than 14 days or dose holds of MPDL3280A for more than 42 days, unless permission from the Sponsor's Medical Monitor for longer dose delay is granted;
- An intercurrent illness that, in the opinion of the Investigator, would affect assessments of the clinical status to a significant degree and requires discontinuation of therapy;
- A positive pregnancy test at any time during the study;
- Investigator decision.

In addition, the Sponsor may discontinue the study early for any of the reasons noted in Section 12.6.

The Sponsor (or designee) should be notified of all study terminations as soon as possible. The date and reason for cessation of PO rociletinib and/or IV MPDL3280A must be documented in the eCRF and source documents.

To the extent possible, EOT assessments should be performed for all patients who receive rociletinib and MPDL3280A. The EOT visit should occur 28 (\pm 7) days after the last dose of rociletinib and MPDL3280A. After stopping protocol-specified treatment, all patients will remain in the study and will be followed for safety (through 28 days after last dose; those with ongoing SAEs will be followed until either resolution or stabilization has been determined), for disease progression (every 8 \pm 1 weeks until disease progression), and for survival status and subsequent NSCLC therapies (at approximately quarterly intervals until death or Sponsor decision).

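### A compliant End-of-Treatment visit on Days 29 to 35 drops out of the laboratory and vital-sign summary tables because those tables stop 28 days after the last dose

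*Combined protocol and SAP*

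**What the plan says.** **Summary window.** Section 10.2.5.3 covers hematology, serum chemistry and urinalysis. It starts the on-treatment period on the day after first dosing and ends it 28 days after the final dose of either drug. Values inside that period feed tables of the maximum, minimum and last value and of the change from baseline to each. For the rest: "The laboratory values collected after the on-treatment period will only be presented in the data listings". Section 10.2.5.4 sets the same period and the same statistics for vital signs, and adds: "The vital sign measurements collected after the on-treatment period will only be presented in the data listings".

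**Visit window.** Section 8.2.2 asks patients to "return to the clinic for the EOT Visit 28 days (+7 days) after the last dose of study treatment". The visit comes earlier if a new anticancer drug is to be started. Table 1 footnote C gives the same timing. Section 11.1 differs: it places the visit at 28 (± 7) "days after the last dose of rociletinib and MPDL3280A".

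**What is measured.** Table 1 schedules hematology, fasting serum chemistry (which includes ALT, AST and bilirubin) and vital signs at the EOT visit. Urinalysis is scheduled at screening only, so it is not affected.

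**The concern.** The summary window closes on the day on which the visit window in Section 8.2.2 and Table 1 opens. Take two patients with the same last-dose date and the same EOT results. If one attends on Day 28 and the other on Day 30, both comply with the protocol, but only the first contributes EOT values to the tables. An abnormality that first appears at the second patient's visit cannot become that patient's maximum or minimum. The last value for that patient is whatever was measured before Day 29.

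What is at stake is the completeness of the descriptive laboratory and vital-sign tables for the one post-treatment safety visit in the schedule. The loss can matter most for patients who stop early, because they have few other scheduled measurements.

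**Working it through.** The plan gives no figure on this point to reproduce. The check is a count of days and a reading of the schedule. Day n means n days after the last dose, and the last dose is taken as the same date in all sections.

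**1. Permitted visit days outside the summary window**

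Share outside = (permitted EOT days after Day 28) / (all permitted EOT days).

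| Source of visit window | Permitted days | Number | After Day 28 | Share |
|---|---|---|---|---|
| Table 1 footnote C; Section 8.2.2: 28 (+7) | 28 to 35 | 8 | 7 (Days 29 to 35) | 7/8 = 87.5% |
| Section 11.1: 28 (± 7) | 21 to 35 | 15 | 7 (Days 29 to 35) | 7/15 = 46.7% |

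This counts Day 28 as inside the summary window, the natural reading of Sections 10.2.5.3 and 10.2.5.4. If Day 28 were counted as outside, the shares would be 8/8 = 100% and 8/15 = 53.3%.

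**2. Does any other provision bring these visits back in?**

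- Table 1 footnote C and Section 8.2.2 allow some collections close to the decision to stop treatment rather than at the visit. This covers the optional biopsy and the PK, pharmacodynamic, TBNK and ATA samples. It does not cover safety laboratory tests or vital signs.
- A visit brought forward to before Day 28 because new anticancer therapy is starting falls inside the window and is summarized.
- No section assigns the EOT visit to the summaries regardless of its date.

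**3. A Phase 2 patient who stops all treatment in Cycle 1**

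- Phase 2 has no run-in, so the first dose is on Cycle 1 Day 1. Section 10.2.5.3 takes the last value on or before that day as baseline, so the Cycle 1 Day 1 panel is baseline.
- Table 1 has no serum chemistry panel on Days 4, 8 or 15 of Cycle 1. Fasting glucose alone is measured on those days. Hematology is measured on Days 8 and 15, and vital signs on all three.
- The next chemistry panel would be on Cycle 2 Day 1, which this patient does not reach. The EOT panel is therefore the only scheduled chemistry after baseline.
- If that visit falls on Day 30 and no unscheduled panel was drawn, the patient has no post-baseline liver tests in any summary table.

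**4. After the change proposed below**

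With the EOT visit included up to Day 35, the share of permitted days outside is 0/8 or 0/15, whichever visit window the sponsor keeps.

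**The case against.** The strongest defense is that 28 days is the protocol's general safety cut-off. Treatment-emergent adverse events end at the last dose plus 28 days (Section 10.2.5.2). Adverse event recording (Section 9.7), the reporting of deaths as serious events (Section 9.2) and concomitant medication recording (Section 7) use the same limit. Extending only the laboratory and vital-sign tables would make a Day 32 value on-treatment while an event starting that day would not be treatment-emergent. This stands as a cost of the change. It does not remove the problem. An adverse event has its own onset date, whereas this is a scheduled visit that is counted or not according to its appointment day. Nor do the adverse event tables fill the gap, because an abnormality with onset after Day 28 is outside them too.

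The second objection is that little depends on these tables. The study is open-label and non-randomized, and the Phase 1 primary endpoints are treatment-emergent adverse events, DLTs and PK. The excluded values are still listed, and separate listings of Grade 3 or 4 laboratory abnormalities are planned. All of this stands and limits the weight of the point.

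A reader might also infer more than the documents support:

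- *That 47% to 88% of patients lose their EOT data.* The documents give no distribution of actual visit days, and deaths, withdrawals and visits brought forward would all alter the count.
- *That all EOT results go to listings.* Visits on Day 28, visits brought forward and, under Section 11.1, visits on Days 21 to 27 are summarized. Under Section 11.1 the excluded days are slightly under half.
- *That thyroid summaries are cut short.* Section 10.2.5.3 names only hematology, serum chemistry and urinalysis, and Section 8.4.2.2 treats thyroid tests separately from chemistry.
- *That the protocol states a concern about late-onset changes after treatment ends.* Its remarks that stopping MPDL3280A may not act at once (Sections 5.7.4, 5.8 and 6.2) concern managing an existing toxicity or an overdose.
- *That after a stop for toxicity the last value is the value at the event.* Section 6.2.3 calls for repeat liver tests every 48 to 72 hours and then weekly for the more marked elevations. Repeats within 28 days of the last dose stay in the window.

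**Conclusion.** The point holds in a limited form. Under every stated visit window, a compliant EOT visit on Days 29 to 35 is excluded from the hematology, serum chemistry and vital-sign summaries by an explicit rule. That is 7 of 8 permitted days under Table 1 footnote C and Section 8.2.2, and 7 of 15 under Section 11.1, counting Day 28 as inside the summary window. The number of patients affected cannot be derived from the documents. The clearest individual consequence is the Phase 2 patient who stops in Cycle 1. If the EOT visit falls late and no unscheduled panel was drawn, that patient has no post-baseline chemistry in the tables.

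The effect is confined to descriptive safety tables. No data are lost, and no primary endpoint or dose decision rests on these summaries. The change is worth making because it is cheap and because the present rule lets the appointment day decide what is reported.

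**What to change.** In Sections 10.2.5.3 and 10.2.5.4, end the summary period at the later of 28 days after the last dose or the protocol EOT visit, with the extension running no further than Day 35 and only up to the start of new anticancer therapy. The new-therapy limit should apply to the extension alone, so that nothing now summarized is removed. If leaving out Day 29 to 35 visits is intended, the plan should say so and give the reason.

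The cost is one sentence in each of two sections, with no new data. The tables would then extend up to 7 days past the treatment-emergent adverse event window, and a footnote should state this.

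Separately, the EOT visit timing in Table 1 footnote C and Section 8.2.2 contradicts that in Section 11.1, and the sponsor must reconcile them. The analysis change works under either window and does not depend on which is kept.

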10.2.5.4 Vital Sign Measurements

The baseline vital sign measurement will be defined as the last value before or on the day of the first dose of either study drug. The on-treatment period will be defined as the day after the first dose of either study drug to 28 days after the last dose of rociletinib or MPDL3280A Vital sign measurements collected during the on-treatment period will be included in the summary tables.

The vital sign measurements collected after the on-treatment period will only be presented in the data listings.

The summary of vital sign data will include descriptive statistics (N, mean, standard deviation, minimum, median, and maximum) of the maximum, minimum, and last value during the on-treatment period by dose group and study phase. Summaries using descriptive statistics of the change from baseline to the maximum, minimum, and last value during the on-treatment period will also be given by dose group.

10.2.5.5 12-Lead Electrocardiograms

Electrocardiogram (ECG) intervals will be stratified into categories indicative of potential clinical significance. Each patient's maximum QT and QT_C intervals from the pretreatment visit and treatment period visits will be classified as $\leq 450 \text{ ms}$, $> 450 \text{ to} \leq 480 \text{ ms}$, $> 480 \text{ to} \leq 500 \text{ ms}$, and > 500 ms. For each patient's maximum change from the pretreatment ECG visit for QT and QT_C, intervals will be classified into < 30 ms, $\geq 30 \text{ to} < 60 \text{ ms}$, and $\geq 60 \text{ ms}$. The number and percentage of patients in each classified category will be presented. Additional endpoints will include abnormal T waves and U waves and other ECG intervals and diagnostic parameters.

Descriptive statistics will be used to summarize other ECG parameters of PR, QRS, QT, and RR interval, and the corresponding changes from pretreatment ECG visit at each time point. Plots of the mean QT/QT_C over time will be provided.

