3.3 Dose Expansion Phase (Phase 2)

The Dose Expansion Phase will be conducted in two patient cohorts (see also Figure 1):

Group A: EGFR TKI treatment-naïve and chemotherapy-naïve patients.

Group B: Patients who have progressed after at least 12 weeks of treatment with a prior firstor second-generation EGFR TKI (ie, erlotinib, gefitinib, afatanib), regardless of T790M mutation status.

The Dose Expansion Phase will be used to assess the RP2D of the combination of rociletinib and MPDL3280A for preliminary efficacy and pharmacodynamics effects, in addition to safety and tolerability, in these patient populations. For the Dose Expansion Phase, there will not be a Run-in-Period; rather, treatment will begin with both rociletinib and MPDL3280A on Cycle 1 Day 1 (C1D1). Patients will receive daily oral BID doses of rociletinib (RP2D) and IV doses of MPDL3280A on Day 1 of each cycle, in consecutive 21-day cycles. Patients will be evaluated regularly for safety and efficacy according to the Schedule of Assessments (see Table 1). For further details on the planned assessments and analyses of safety, PK, efficacy and pharmacodynamics, please refer to Sections 8.4.2-8.4.5.

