The initial dose of MPDL3280A will be delivered over 60 (\pm 15) minutes. If the first infusion is tolerated without infusion-associated AEs, the second infusion may be delivered over 30 (\pm 10) minutes. If the 30-minute infusion is well tolerated, all subsequent infusions may be delivered over 30 (\pm 10) minutes. For the first infusion, the patient's vital signs (heart rate, respiratory rate, blood pressure, and temperature) should be determined within 60 minutes before the infusion, every 15 [\pm 5] minutes during the infusion, and 30 (\pm 10) minutes and 2 hours (\pm 15 minutes) after completion of the infusion. For subsequent infusions, vital signs will be collected within 60 minutes before the infusion, during the infusion as clinically indicated or if symptoms occurred in the prior infusion, and 1 hour (\pm 10 minutes) after the infusion.

No premedication will be allowed for the first dose of MPDL3280A. Premedication may be administered for subsequent infusions at the discretion of the treating physician after consultation with the Medical Monitor.

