8.4.2.3 Vital Signs

Vital signs will be measured at all clinic visits as outlined in Table 1. Vital signs include body temperature, heart rate, respiratory rate, and blood pressure. All vital signs will be obtained after the patient has been resting for at least 5 minutes.

Weight will also be measured at all clinic visits as part of physical examinations (see Section 8.4.2.6).

For the first infusion of MPDL3280A, vital signs should be measured within 60 minutes before, every 15 (\pm 5) minutes during the infusion, and 30 (\pm 10) minutes after the infusion. For subsequent infusions, vital signs will be collected within 60 minutes before the infusion, during the infusion if clinically indicated or if symptoms occurred in the prior infusion, and 1 hour (\pm 10 minutes) after the infusion.

8.4.2.4 12-Lead Electrocardiograms

Triplicate serial 12-lead ECGs (10-sec ECG tracings collected in triplicate > 2 min apart) will be taken at time points specified in Table 1 and as clinically indicated. The average of triplicates should be recorded.

Electrocardiograms should be performed after the patient has been resting for at least 5 min. The 12-lead ECGs collected will be read locally to facilitate patient management and analyzed at a central ECG laboratory. Details on recording ECGs and their interpretation will be included in the Investigator's file.

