10.2.5.2 Adverse Events

Adverse event (AE) coding will be performed using MedDRA terminology. The severity of the toxicities will be graded according to the NCI CTCAE v4.03 whenever possible. Treatmentemergent AEs are defined as AEs with an onset date on or after the date of first dose of rociletinib or MPDL3280A until the date of the last dose of either study drug plus 28 days. AEs will be considered treatment-emergent if all or part of the date of onset of the AE is missing and it cannot be determined if the AE meets the definition for treatment-emergent.

The number and percentage of patients who experienced treatment-emergent AEs for each system organ class and preferred term will be presented by dose group. Multiple instances of the treatment-emergent AEs in each System Organ Class and multiple occurrences of the same Preferred Term are counted only once per patient. The number and percentage of patients with at least one treatment-emergent AE will also be summarized by dose group.

Separate tables will present the following by dose group and study phase:

- All treatment-emergent AEs;
- Treatment-emergent AEs by CTCAE grade;
- Grade 3 or greater treatment-emergent AEs;
- Grade 3 or greater treatment-related, treatment-emergent AEs;
- Treatment-related, treatment-emergent AEs;
- Dose-limiting toxicity AEs;
- Serious treatment-emergent AEs;

- Serious treatment-related, treatement-emergent AEs;
- Treatment-emergent AEs with an outcome of death;
- Treatment-emergent AEs leading to discontinuation of either study drug;
- Treatment-emergent AEs resulting in interruption or reduction of either study drug.

The incidence of treatment-emergent AEs will be summarized by relationship to oral study drug using "treatment-related" and "not treatment-related" categories. If a patient experiences multiple occurrences of the same AE with different relationship categories, the patient will be counted once as a relationship category of treatment-related.

If a patient experiences multiple occurrences of the same AE with different intensity toxicity grades, the patient will be counted once for the maximum (most severe) toxicity grade. AEs with a missing intensity will be presented in the summary table with a toxicity grade of "Missing." For each toxicity grade, the number and percentage of patients with at least one treatment-emergent AE of the given grade will be summarized.

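### In Phase 2 the vital-sign summaries leave out every reading taken during and after the first MPDL3280A infusion, and the baseline rule has no pre-dose condition

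*Combined protocol and SAP*

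**What the plan says.** Section 10.2.5.4 gives two rules. For baseline: "The baseline vital sign measurement will be defined as the last value before or on the day of the first dose" of either study drug. For the analysis window: "The on-treatment period will be defined as the day after the first dose of either study drug", running to 28 days after the last dose. Values inside that window go into the summary tables (maximum, minimum and last value, and the change from baseline to each). Values collected after the window go to listings only.

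Section 3.3 states that Phase 2 has no run-in and that both drugs start on Cycle 1 Day 1 (C1D1). Phase 1 has a 7-day rociletinib run-in before the first infusion (Section 3.2).

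That first infusion is closely monitored. Section 8.4.2.3 begins: "For the first infusion of MPDL3280A, vital signs should be measured within 60 minutes before". It goes on to require readings every 15 minutes during the infusion and one 30 minutes after it. Table 1 footnote J says the same. Section 5.3 adds a reading 2 hours after the infusion ends.

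Section 10.2.5.2 uses a different window for adverse events. Treatment-emergent events are "AEs with an onset date on or after the date of first dose of rociletinib or MPDL3280A", so Day 1 is included.

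**The concern.** The first infusion carries the densest scheduled vital-sign monitoring in the study, and Section 5.3 allows no premedication for it. In Phase 2 it falls on the first-dose day. A window that opens the next day therefore omits these readings from the tables meant to summarise vital signs on treatment. The baseline rule, which names a day and no time, can also select a reading taken after both drugs have been given. Changes from such a baseline would not measure change from an untreated state, and they would not mean the same thing in Phase 2 as in Phase 1.

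**Working it through.** The plan gives no figure to reproduce. The check places the scheduled C1D1 readings on a timeline and applies Section 10.2.5.4 as written.

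**Inputs**
- The infusion starts about 120 minutes after the morning rociletinib dose (Section 8.4.4; Table 2 footnote e).
- The first infusion lasts 60 (±15) minutes (Section 5.3).
- Readings are taken within 60 minutes before, at a nominal 15-minute spacing during, and 30 minutes after (Section 8.4.2.3; Table 1 footnote J). Section 5.3 adds one at 2 hours after.

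**Step 1: number of readings during and after the infusion.** During = duration ÷ 15, counting the one at the end. After = 1 under Section 8.4.2.3, or 2 under Section 5.3.

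**Step 2: time of the last C1D1 reading, in minutes after the first rociletinib dose.** This is 120 + duration + 30 under Section 8.4.2.3, or 120 + duration + 120 under Section 5.3.

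| Infusion (min) | During | During + after: 8.4.2.3 / 5.3 | Last reading (min): 8.4.2.3 / 5.3 |
|---|---|---|---|
| 45 | 3 | 4 / 5 | 195 / 285 |
| 60 | 4 | 5 / 6 | 210 / 300 |
| 75 | 5 | 6 / 7 | 225 / 315 |

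**Step 3: the window.** All these readings fall on the first-dose day, and the window opens the day after. For a 60-minute infusion, 0 of the 5 (or 6) count as on-treatment values. Section 10.2.5.4 sends only values after the window to listings, so these Day 1 readings are assigned to no stated output, apart from any one that becomes baseline.

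**Step 4: the baseline.** Read literally, the last value on the first-dose day is the one at about 210 minutes (Section 8.4.2.3) or 300 minutes (Section 5.3) after rociletinib. The disagreement between those sections decides which. The pre-infusion reading is not drug-free either: it falls between 120 − 60 = 60 and 120 minutes after rociletinib.

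**Step 5: Phase 1 against Phase 2.** With the run-in, the first infusion comes about 7 days after the first dose and its readings are on-treatment. That does not hold for the optional safety expansion cohort of up to 6 patients, which may be dosed without a run-in (Section 3.2.3). Section 10.2.5.4 presents the maximum, minimum and last values by dose group and phase, but the vital-sign changes from baseline by dose group only. If Phase 2 uses a Phase 1 dose, that table can mix the two kinds of baseline.

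**Step 6: share of patients.** Section 4.1 plans 75 Phase 2 patients of 93 in total: 75 ÷ 93 = 81%. Any expansion-cohort patients without a run-in come on top.

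**The case against.** The best defence concerns the baseline. Table 1 footnote A places assessments before study treatment where applicable, so a C1D1 pre-dose reading can be taken as the intended baseline. A reader might infer that the plan definitely adopts a post-infusion baseline, and the documents do not support that much. They leave it open: footnote A is general, footnote J requires later readings the same day, and Section 10.2.5.4 has no time condition. The defence does not reach the window. Even with a pre-dose baseline, readings during and after the first infusion stay outside it.

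A reader might also infer that infusion reactions in Phase 2 would go unseen. They would not. Treatment-emergent events count from the first-dose date. Section 9.6 lists infusion-reaction, hypersensitivity and cytokine-release events as being of special interest, to be recorded within 24 to 48 hours. The Clinical Safety Committee reviews safety data in both phases (Section 3.1). Vital signs are not a listed endpoint, and their analysis is descriptive.

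Nor does the laboratory section share the problem to any real extent. Section 10.2.5.3 uses the same wording, but Section 8.4.2.2 requires results to be reviewed before dosing, so those samples are generally pre-dose.

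**Conclusion.** The point holds for the analysis window on any reading of the text. In Phase 2, and in any Phase 1 expansion cohort without a run-in, no reading during or after the first infusion enters the vital-sign tables as an on-treatment value. That is about 5 readings per patient, or 6 under Section 5.3, for a 60-minute infusion, in up to 75 of 93 planned patients. For the baseline the finding is narrower: the literal rule selects a post-infusion value, a pre-dose intention is plausible, and the text does not settle it.

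The consequence is limited to the descriptive vital-sign summaries, their inconsistency with the adverse-event window, and comparability between phases. Safety capture through adverse events and the response-rate analysis are untouched. The counts assume nominal reading times and the stated order of the two drugs. The documents give no vital-sign data, so the size of any shift in reported blood pressure or heart rate cannot be estimated. It should be corrected before the analysis is programmed.

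**What to change.** In Section 10.2.5.4, define baseline as the last value before the first dose of either study drug: the pre-rociletinib reading on that day, otherwise the screening value. Start the on-treatment period at the first dose, so that post-dose Day 1 readings are included. The screening fallback matters because Table 1 footnote B lets Day 1 procedures be omitted when recently done.

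Use the same wording in Section 10.2.5.3, for consistency only.

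Reconcile Section 5.3 with Section 8.4.2.3 and Table 1 footnote J on the 2-hour post-infusion reading, so that all sites collect the same set.

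The cost is small but not nil. Vital-sign clock times relative to dosing must be recorded. Section 8.4.4 asks for the times of pharmacokinetic draws, meals and drug administration, but not of vital signs. Settling the 2-hour reading also means amending at least one procedural passage. The rest is analysis wording.
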